Summary tables were provided for prior/concomitant medications in the study.

Immunogenicity analyses

Partial correlation was used to measure the relationship between the percent change in HbA1c and percent change in anti-insulin antibodies with absolute change in total insulin dose as covariate from baseline to Visit 7 and Visit 8. Change in level of serum anti-insulin antibodies from baseline to Visit 7 and Visit 8 were compared through paired t-test within each treatment arms.

Statistical Significance

The level of significance in the primary analysis were set to 5%. The analyses was performed upon completion of the main trial period. All secondary analyses were also be performed at the 5% significance level.

Replacement of Subjects

The subject who discontinued from trial/withdrawn from the study treatment were not replaced.

Withdrawn Subject Data Collection

The subject could withdraw their consent from the trial, or this could be the Investigator's decision to discontinue the subject from trial; if they decided to do so, at any time and irrespective of the reason all efforts should be made to document the reason for treatment withdrawal/discontinuation from the trial (see section 11.5.1) and this should be documented in the e-CRF.

The Investigator/designee involved in the study documented the reason for the subject withdrawal as follows:

Subject's voluntary withdrawal of consent

Subject's non-compliance to the IP: Repeated missing of study medication doses

Protocol violation: Repeated non-follow-up for safety or efficacy procedures required for the study. Protocol violation may be also considered when the subject is not included as per protocol-defined eligibility criteria.

Any AE or SAE requiring subject withdrawal in the opinion of the Investigator: An AE form must be completed. Clinically significant abnormal value not explained by a laboratory error or being not a known or abnormal value commonly observed in this type of population was also considered as an AE or SAE, and recorded on AE form as applicable.

Requirement of prohibited medication: Recording of the details of prohibited medication were completed on the concomitant medication CRF page and the subject were withdrawn from the study.

Requirement of dose reduction for both IP and non-IP: If there was requirement for change in dose of the IP (which is not mentioned in the protocol) or non-IP at any point of time during the study period, the subject were withdrawn from the study.

Study termination by Sponsor: Upon notification of the sponsor for termination of the study

Study termination based on the advice by CDSCO or any other competent authority: If the regulatory authority(ies) directly connects to the site/CRO to terminate the study, the same was immediately done by the Investigator/information were communicated to the sites. The CRO must notify the site regarding such communications. In case of communications directly reaching the Investigator, the Investigator must inform the CRO designee (e.g. study site monitor) or both Sponsor designee and CRO designee

Any, other reason: If none of the above-mentioned reasons are applicable, then the reason for subject withdrawal were mentioned; "any other reason" and the reason were specified on the eCRF page. In case of pregnancy, the subject's study treatment must permanently stop and study discontinuation and early withdrawal procedures should be conducted.

Determination of Sample Size

It was estimated that 52 evaluable subjects per dose group were needed to be enrolled in each treatment group assuming a reduction of 0.5 in HbA1c, common standard deviation (SD) of 1.0 at baseline and at Week 12 in each dose group with 90% power and 2.5% level of significance. However, 13 extra subjects, accounting for 65 subjects per group in total were enrolled into this study with an aim to compensate for an estimated drop-out rate of 20%. Thus, a total number of 195 subjects were to be randomly assigned to either of the three dose (treatment) groups in this study in the ratio of 1:1:1. The detailed description of sample size calculation is represented in the table below:

Single Mean - Paired t-test				
Pre-test mean	7.5			
Post-test mean	7			
Mean Difference from Pre-to Post test	0.5			
Standard deviation in Pre-test	1			
Standard deviation in Post-test	1			
Effect size	0.5			
Power (%)	90			
Alpha Error	2.5			
1 or 2 sided	2			
Minimum required sample size for each selected fixed dose treatment	52			

group	
Minimum required sample size for all three-selected fixed dose treatment	156
groups	
Considering 20% drop-out, required sample size for each selected fixed	65
dose treatment group per	
Considering 20% drop-out, required sample size for all three-selected	
fixed dose treatment groups	195

Missing Data

The missing observations were imputed using Last Observation Carried Forward (LOCF) appropriately.

Procedures for Reporting Deviations from Original Statistical Plan

Any post-hoc, or unplanned, analyses not identified in SAP were clearly identified in the respective clinical study report (CSR).

Change in Conduct of the Study and Planned Analysis

Changes in Conduct of the Study

Following changes were made in conduct of study due to COVID-19 pandemic and nationwide lockdown implemented by Government of India:

- The home visits were arranged by investigator sites for laboratory sampling. The samples were processed in local hospital labs or central lab's local centres.
- Due to home visit physical examination and vital sign were not performed for these subjects and protocol deviations were filed.
- Telephonic contacts by the site team was done to record the AEs, concomitant medications and subject's clinical status as an alternate option to clinical visit. The participants whose blood samples were collected (hospital visit/home visit) within the one week of window period, were considered in the per-protocol population.

For site No. 20, the protocol approval was received however site initiation visit was not done because of nation-wide lockdown by the government of India due to COVID-19 Pandemic.

Change in Planned Analysis

Not applicable.

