- AE/SAEs (including details of hypoglycaemic episode)
- Concomitant medications

- Subject diary was collected and reviewed at each visit (Visits 3 to 6)
- Subject diary was dispensed at each visit (Visits 3 to 6)
- Accountability and compliance check of IP
 - Accountability check was done by recording number of capsules dispensed to the subjects (as per the dose) versus number of capsules used and/or the number of capsules lost/destroyed in the accountability log
 - Compliance check was done by calculating number of capsules (as per dose dispensed) consumed by the subject versus total capsules required to be consumed
- Laboratory investigations
 - Fasting plasma glucose (at Visits 3, 4 and 6 only)
 - 2-hours postprandial plasma glucose (at Visits 3, 4 and 6 only)
- Dispensing of IP at Visits 3, 4, 5, and 6 as per the treatment groups:
 - Subjects in Group A were dispensed USVCAP capsules of dose strengths 75 IU at each visit up to Visit 6 and were prescribed 1 capsule of USVCAP (i.e. assigned fixed dose: 75 IU, BD) orally twice daily before breakfast and dinner at each scheduled visit until 1 day prior to next scheduled visit (i.e. Visit 7/Day 85 [+2 days])
 - Subjects in Group B were dispensed USVCAP capsules of dose strength 150 IU at each visit up to Visit 6 and were prescribed 1 capsule of USVCAP (i.e. assigned fixed dose: 150 IU, BD) orally twice daily before breakfast and dinner until 1 day prior to next scheduled visit (i.e. Visit 7/ Day 92 [+2 days])
 - Subjects in Group C were dispensed USVCAP capsules of dose strength 150 IU at each visit up to Visit 6 and were prescribed 2 capsules of USVCAP (i.e. assigned fixed dose: 300 IU, BD) orally twice daily before breakfast and dinner until 1 day prior to next scheduled visit (i.e. Visit 7/ Day 99 [+2 days])

Visit 7 (End-of-treatment visit)

This was the EOT visit for all subjects. It occurred on the next day after the subject had completed administration of twice daily doses of assigned fixed dose IP for 12 weeks. The following procedures and assessments were performed at this visit:

- The following details should be recorded at this visit
 - Findings of physical examination
 - \circ Body weight (kg), waist circumference (cm), and body mass index (BMI) (kg/m²)
 - Vital signs: SBP and DBP (mmHg), PR [beats/min], RR [breaths/min] in supine position after 5 min of rest and body temperature (°F)
 - Change in concomitant medications, if any

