The safety of USVCAP formulation in Type 2 Diabetes Mellitus Subjects Uncontrolled with Metformin Hydrochloride Treatment was determined by incidence and severity of treatment emergent adverse events (TEAEs) that occurred during the study period, including occurrence of hypoglycaemic episodes in each treatment group during the study period; and change in laboratory investigations post 12-week administration of USVCAP. Efficacy of the treatment was assessed by change in glycated haemoglobin (HbA1c) level post 12-week twice daily administration of selected fixed dose of USVCAP (75 IU, or 150 IU or 300 IU) from baseline, comparison of change in HbA1c between the 3 fixed dose levels studied to examine dose response relationship post 12-week administration of USVCAP and change in FPG and 2-hour PPG levels in each treatment group post 12-week administration of USVCAP. The immunogenicity was assessed by evaluating incidence of treatment-emergent antibody response (TEAR).

Selection of Study Population

Inclusion Criteria

- 1. Male or female aged 35 to 60 years (both inclusive)
- 2. Type 2 diabetes mellitus diagnosed < 2 years prior to enrolment
- 3. Glycated haemoglobin level $\ge 7\%$ and $\le 9.5\%$
- 4. On stable oral monotherapy with metformin hydrochloride (1000 mg to 2500 mg/day) and regular diet and exercise regimen at least 12 weeks prior to enrolment
- 5. Body mass index between 18 to 30 kg/m2
- 6. Ability to perform capillary blood glucose measurements

- 7. Willing to provide informed and written consent for the clinical trial
- 8. Able to comply with all requirements of clinical trial protocol

Exclusion Criteria

- 1. Subject with history or evidence of hypersensitivity to insulin or metformin hydrochloride or its excipients
- 2. Suffering from type 1 diabetes mellitus
- 3. Received treatment with sulphonylureas or alphaglucosidase inhibitors, Glucagon-like peptide-1 (GLP-1) receptor agonists or Sodium-glucose co-transporter 2 (SGLT2) inhibitors or meglitinides or pramlintide or thiazolidinediones within 3 months prior to enrolment
- 4. Previously treated with insulin within 3 months prior to enrolment
- 5. History of episodes of hypoglycaemia during 3 months prior to enrolment.
- 6. Reduced awareness of hypoglycaemia or inability to identify and tackle hypoglycaemic episodes
- 7. History of substantial weight loss defined as 5% decrease in body weight within the last 6 months
- 8. Medical history of unstable angina within 1 year prior to enrolment

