- 25. Has any concurrent disease or medical/surgical condition, which required treatment of more than 3 months and which in the opinion of the Investigator does not allow participation of the subject in this study.

Study Specific Discontinuation/Withdrawal Criteria

The subjects could withdraw their consent to continue participation in the study without providing any reason, or the Investigator could decide in the interest of the safety of the subject to withdraw the subject from trial at any time during the study period.

The subject was withdrawn from the study treatment or discontinued from the trial due to any one of the following reason:

- Subjects' voluntary withdrawal of consent
- Protocol violation
- Subject's non-compliance to the administration of IP as per the protocol
- Any AE or SAE requiring withdrawal of subject in the opinion of the Investigator
- Requirement of prohibited concomitant medication
- Requirement of dose reduction for both IP and non-IP
- Study termination by the Sponsor
- Study termination based on the advice by CDSCO or any other competent authority
- Subjects who experience 2 or more than 2 episodes of hypoglycaemia within a day
- Subjects diagnosed with uncontrolled hyperglycaemia as defined in the protocol

The Investigator discussed with the subject, the most appropriate way to withdraw from the study to ensure the subject's health and safety. The subject was called to visit the study site and all study assessments and procedures were performed as per the EOT visit (i.e. Visit 7) (Table 3). In case of an ongoing SAE, the subjects were followed up till recovery or stabilization of SAE, whichever was appropriate without compromising on subject's safety.

STUDY TREATMENT OF SUBJECTS

Treatment Administered

- Group A: USVCAP 75 IU, BD for 12 weeks
- Group B: USVCAP 150 IU, BD for 12 weeks
- Group C: USVCAP 300 IU, BD for 12 weeks

Investigational Product

The investigational product, USVCAP was administered at doses 75 IU, 150 IU, and 300 IU, orally, twice daily.

Dosage form: It was supplied by the sponsor as 75 IU and 150 IU capsules for oral administration.

Dosage: Each subject allocated to treatment Groups A, B, or C received treatment with USVCAP IP as follows:

For subjects randomized to Group A (USVCAP 75 IU BD for 12 weeks) administered the IP as follows:

USVCAP 75 IU BD: Day 1 until Day 84

For subjects randomized to Group B (i.e. USVCAP 150 IU BD for 12 weeks) and Group C (i.e. USVCAP 300 IU BD for 12 weeks):

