There was a run-in period/s of 1 week with each lower dose/s prior to initiation of the assigned fixed dose of USVCAP (Table 2). Upon completion of the run-in period/s, the subjects received the assigned fixed dose of USVCAP further for 12 weeks.

The Investigator considered the dose increase for each subject in Group B and Group C only if there was no evidence of lack of tolerability with dose/s of IP prescribed during run-in period/s and that the safety of the subject was unlikely to be compromised after administration of subsequent higher dose/s of the IP.

The dose increase at each DE visit was considered only after laboratory test results for FPG and 2-hour PPG levels were available to the Investigator.

For subjects in Group B (USVCAP 150 IU BD for 12 weeks):

- Run-in period
 - USVCAP 75 IU BD: Day 1 until Day 7
- Treatment period
 - USVCAP 150 IU BD: Day 8 until Day 91

For subjects in Group C (USVCAP 300 IU BD for 12 weeks):

- Run-in periods
 - USVCAP 75 IU BD: Day 1 until Day 7: 75 IU BD
 - USVCAP 150 IU BD: Day 8 until Day 14
- Treatment period
 - USVCAP 300 IU, BD: Day 15 until Day 98

The USVCAP doses were administered as per the trial protocol until the EOT. The subjects were withdrawn from the trial if there was requirement for change in dose during the treatment period (including run-in period and/or assigned fixed dose period), due to any reason(s).

Mode of administration: 1 hour before breakfast and dinner, orally with water

Duration of Treatment:

Treatment period: Each subject was treated with assigned fixed dose of USVCAP (Group A or Group B or Group C) for 12 weeks.

Overall duration of treatment with IP (including run-in period/s):

- Group A=12 weeks
- Group B=13 weeks
- Group C=14 weeks

During the post-treatment follow-up period, subjects were advised treatment for T2DM as per standard treatment guidelines.

Non-investigational Product

It was metformin hydrochloride capsules 250 mg, 500 mg, 850 mg or 1000 mg doses.

Dosage: Subjects continued their pre-study oral anti-diabetic monotherapy (i.e. metformin hydrochloride) as per pre-study dose and regimen from screening until the EOT, the dose adjustment for which, was not allowed during the entire treatment period.

Mode of administration: Orally with water along with meals

Duration of Treatment

• Approximately 17-19 weeks based on the randomized treatment group (i.e. Group A, Group B, or Group C).

Treatment during Post-Treatment Follow-Up Period:

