The efficacy assessments HbA1c, FPG and 2-hour PPG were assessed at the central laboratory identified for the study.

It was performed as follows:

- At screening to confirm the eligibility of the subject in the study
- During the treatment period and at EOT to evaluate to assess the safety and the treatment response
- At the EOS to evaluate the post-treatment safety of the subjects after twice daily administration of IP for 12 weeks

The blood samples for HbA1c, FPG and 2-hour PPG were withdrawn from the subject for the following tests:

- Glycated haemoglobin at Visit 1 and Visit 7
- Fasting plasma glucose level under fasting condition i.e. at least 8–10 hours of overnight fasting at Visits 1, 3, 4, 6, and 7 for all subjects

For Group B subjects: Prior to Visit DE 1

For Group C subjects: Prior to Visit DE 1 and Visit DE 2

• Postprandial glucose level (2-hours after meal) at Visits 1, 3, 4, 6 and 7 for all subjects. For Group B subjects: Prior to Visit DE 1

For Group C subjects: Prior to Visit DE 1 and Visit DE 2

• All samples were sent to central laboratory for evaluation. FPG and 2-hour PPG test results at Visit DE 1 and Visit DE 2 should be available prior to dosing.

Capillary glucose measurements

Capillary glucose measurements were performed by the subjects using a self-monitoring blood glucose device throughout the treatment period (from Visit 2 to Visit 7), once every week (mid-week).

During run-in period(s) (from Visit 2 to DE 1 [in Group B subjects] and from Visit 2 to Visit DE 1 and from Visit DE 1 to Visit DE 2 [in Group C] subjects), capillary glucose measurements were performed at mid-week.

The capillary glucose measurements were performed at the following 4 time points:

- Fasting: After 8 hours of overnight fast
- 2-hours post-breakfast
- 2-hours post-lunch
- 2-hours post-dinner

The measurements for all 4 timepoints were performed on the same day. All capillary glucose measurements were recorded by subject in the respective visit subject diary.

Hypoglycemia

It was important for subjects in the study to recognize signs and symptoms of hypoglycemia. Subjects enrolled in the study were educated on signs and symptoms of hypoglycemia and were instructed to keep glucose tablets handy & take 4 glucose tablets (total 15 -20 grams of glucose) immediately to treat hypoglycemia, if it occurs.

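### The end-of-treatment 2-hour PPG is drawn the day after the last USVCAP dose, so it does not measure the effect of a pre-meal dose and may understate it

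*Combined protocol and SAP*

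**What the plan says.** Under Mode of administration, USVCAP is taken "1 hour before breakfast and dinner, orally with water". The Dosage text ends treatment on a fixed calendar day in each arm: "USVCAP 75 IU BD: Day 1 until Day 84" for Group A, "USVCAP 150 IU BD: Day 8 until Day 91" for Group B and "USVCAP 300 IU, BD: Day 15 until Day 98" for Group C. Table 2 puts Visit 7 on Day 85, 92 and 99, and the visit description confirms the order: "It occurred on the next day after the subject had completed administration of twice daily doses of assigned fixed dose IP for 12 weeks". Table 2 shows capsules dispensed up to Visit 6 and none at Visit 7.

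The Efficacy Assessment section schedules "Postprandial glucose level (2-hours after meal) at Visits 1, 3, 4, 6 and 7 for all subjects". It does not name the meal and says nothing about a USVCAP dose before it. The Discussion of Study Design counts "change in FPG and 2-hour PPG levels in each treatment group post 12-week administration of USVCAP" among the efficacy measures. The 2-hour PPG is listed under Primary Variable(s), and Secondary Analysis applies to it the ANCOVA described for HbA1c.

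Visit 7 may be up to 2 days late. For the last supply, the section on Visits 3 to 6 has Group A take capsules "until 1 day prior to next scheduled visit (i.e. Visit 7/Day 85 [+2 days", with parallel wording for Groups B and C.

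**The concern.** For a product dosed ahead of a meal, the 2-hour PPG is the measurement closest to what the dose is meant to do. The plan places the final PPG on the first day without a dose. This is the planned procedure in all three arms, not a deviation by some subjects.

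A value taken without the pre-meal dose may lie nearer to baseline than one taken with it. If so, the PPG change within each arm is understated, and differences between 75, 150 and 300 IU are narrowed. There is no placebo arm, so the contrast between doses is the only randomised efficacy evidence on PPG. A weak Visit 7 result could then be read as absence of a post-meal effect when the sampling day contributed to it.

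**Working it through.** **1. The plan's own 12 weeks.** Days at the assigned dose = last day − first day + 1. Gap = Visit 7 day − last dosing day. Inputs: the Dosage text and Table 2.

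| Group | Days at assigned dose | Visit 7 | Gap (days) |
|---|---|---|---|
| A | 84 − 1 + 1 = 84 | Day 85 | 85 − 84 = 1 |
| B | 91 − 8 + 1 = 84 | Day 92 | 92 − 91 = 1 |
| C | 98 − 15 + 1 = 84 | Day 99 | 99 − 98 = 1 |

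The stated 12 weeks is reproduced in every arm, and Visit 7 is one day past it.

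**2. Hours from last dose to sample.** The last dose precedes dinner by 1 hour on the day before Visit 7. If the PPG follows the first meal on Visit 7 (an assumption, since the meal is not named), the interval is at least 1 + length of fast + 2 hours, ignoring time spent eating.

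- Dosed breakfast on regimen: 1 + 2 = 3 h.
- Visit 7 with the general fast of 8 to 10 h (Laboratory Investigations): 1 + 8 + 2 = 11 h to 1 + 10 + 2 = 13 h.
- Visit 7 with the 12 h fast for the lipid profile: 1 + 12 + 2 = 15 h.

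A later meal lengthens the Visit 7 interval.

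**3. A late Visit 7.** Take Group A on Day 85 + 2 = 87.

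- If capsules run to the day before the actual visit, the last dose is on Day 86. The interval stays at 11 to 15 h, but dosing lasts 86 days rather than 84.
- If dosing stops on the calendar day, the last dose is on Day 84. The interval is 11 + 48 = 59 h to 15 + 48 = 63 h, and 2 + 2 + 1 = 5 scheduled dosing times pass before a post-breakfast sample.

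The Visit 7 meal is undosed on either reading.

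**4. Size of the loss.** The documents give no duration of action, no expected PPG effect and no SD for PPG; the sample size rests on HbA1c alone. The loss therefore cannot be computed. As illustration only: if a fraction f of the meal effect remained at Visit 7, equally in all arms and with the SD unchanged, the number of subjects needed to detect it would rise by 1/f².

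| f (assumed) | 1/f² |
|---|---|
| 0.75 | 1.8 |
| 0.50 | 4 |
| 0.25 | 16 |

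**5. Where Visit 6 falls.** Visit 6 day minus run-in days: 60 − 0 = 60 (A), 67 − 7 = 60 (B), 74 − 14 = 60 (C). Visit 6 is day 60 of the assigned dose in every arm.

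**The case against.** The strongest reply is that the Visit 7 value is still informative and that little depends on it. The primary endpoint is HbA1c, tested within each arm by a paired t-test, and the trial is sized on it. PPG is analysed in one sentence under Secondary Analysis. Dose response is defined explicitly only for HbA1c. The ANCOVA includes visit and its interaction with treatment, so estimates at Visits 3, 4 and 6 are available, and subjects also record weekly post-meal capillary values. The screening PPG was undosed too, so Visit 7 against Visit 1 could show a residual or indirect effect of 12 weeks of treatment.

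Most of this stands and limits the weight of the point. It does not answer it: a residual effect is not the effect of a dose taken before that meal, and the plan does not label the Visit 7 PPG as a residual measure.

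Four stronger readings are tempting but not supported.

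- *That Visits 3, 4 and 6 are on-dose and only Visit 7 is not.* Those visits lie within the dosing period, but no text confirms a dose before the sampled meal on those days. If the meal were lunch, the regimen would put no dose directly before it.
- *That Visit 7 shows none of the meal effect, or some stated share of it.* Without a duration of action, any percentage is an assumption.
- *That the interval is typically about 60 hours.* That needs a late visit and the calendar reading of when dosing ends. The definition of Visit 7 and the dispensing text both tie the last dose to the day before the visit, so this is the less supported reading.
- *That the FPG is equally compromised.* On the nominal day the previous evening's dose precedes it.

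**Conclusion.** The point holds, and it is confined to the end-of-treatment PPG. By the plan's own calendar, every subject who follows it gives the Visit 7 2-hour PPG one day after the last dosing day, after a meal with no USVCAP dose before it. The resulting change does not measure the effect of a pre-meal dose. It may understate that effect and narrow any between-dose PPG contrast taken from the ANCOVA. The timing is certain; the direction is an inference from pre-meal dosing; the size is unknown. The 11 to 15 hour interval assumes that the sample follows the first meal of the day.

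The primary HbA1c endpoint is unaffected. A reader might infer that the primary efficacy result or the HbA1c dose comparison is undermined; nothing in the documents supports that. The change is worth making because a listed efficacy variable is measured on the wrong side of the last dose and the remedy is small.

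**What to change.** **Sampling.** Leave the dosing as it is. Draw the end-of-treatment 2-hour PPG on the last dosing day (Day 84, 91 or 98), after a meal preceded by that day's scheduled dose. Name the meal, and record the dose and meal times. The cost is one planned sample moved by one day, which may mean a separate attendance if the other Visit 7 bloods stay where they are.

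**Data already collected.** Label the Visit 7 PPG as off-dose, and do not use it alone to conclude on post-meal effect or on PPG differences between doses. Report PPG from Visits 3, 4 and 6 as on-treatment only for subjects whose diary confirms a pre-meal dose that day. Identify this as post hoc in the study report, as the section on deviations from the statistical plan requires. The cost is a diary check, a relabelled table and an additional one. The on-treatment PPG would then reflect about 60 rather than 84 days at the assigned dose, in a subset that depends on diary completeness.

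**Reconciliation.** The Dosage text (dosing ends on a fixed day) and the dispensing text for Visits 3 to 6 (dosing runs to the day before Visit 7, window included) must be reconciled for a late Visit 7, so that the interval from last dose to sample is defined.
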